9.1 Variables and derivations

End of trial classifications are defined as follows:

- Screening failure:

Participants who consent to participate in the clinical study but are not subsequently entered in the study & do not meet the criteria for participation in the study.

- Completed trial:

All participants who completed the trial, as indicated in the end of study: Trial Disposition page of eCRF form, will be assumed to have completed trial.

- Lost to follow-up:

A participant will be considered lost to follow-up if he or she repeatedly fails to return for scheduled visits and is unable to be contacted by the study site. Site personnel or designee are expected to make diligent attempts to contact participants who fail to return for a scheduled visit or were otherwise unable to be followed up by the site.

The following parameters will be summarized for the Participant's disposition table as per eCRF:

- Number of screened participants
- Screening status
 - Entered into trial
 - Failed
- Screen failure reasons
- Number of participants in screened population
- Number of participants in enrolled population
- Number of participants in Intent-to-Treat population
- Number of treatment completed participants
- Number of study ongoing participants
- Number of treatment discontinued participants
- Reason of treatment discontinued participants
- Number of study completed participants
- Number of study withdrawn participants
- Reason of study withdrawn

Note- Subjects may have only one primary reason.

Participants who completed the study, as indicated on the “End of Study: Trial Disposition” form of the (eCRF), will be assumed to have completed the study. And participants who completed the treatment, as indicated on the “Study Treatment Discontinuation: Treatment Discontinuation” form of the (eCRF), will be assumed to have completed the treatment. (i.e., participants who completed the trial will be counted under both the “completed treatment” and “completed trial” category).

The following parameters will be summarized for the study discontinuation table as per eCRF Participant's primary reason for discontinuation (reasons mentioned in eCRF end of study form) which is as follows:

- Adverse event
- Death
- Lost to follow-up
- Pregnancy
- Protocol violation
- Screen failure
- Consent withdrawal not due to an adverse event
- Study terminated by sponsor
- Migration from the study site such that follow up visits are not possible
- Other

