Participants who have consented meet all the eligibility criteria and who have successfully completed all protocol procedures at screening will receive the following study intervention for 12 weeks:

FF/UMEC/VI 100mcg/62.5mcg/25mcg via the ELLIPTA inhaler once daily in the morning

On the morning of study clinic Visit 2 (start of treatment), Day 28 (Visit 3) and telephonic contact Day 84 (telephonic Visit 4), participants will refrain from taking their morning dose of study intervention/COPD medication until instructed to do so by clinic personnel. Participants will take their last dose of study treatment on Day 84 and will return for their final clinical assessments on Day 85 (Visit 5). A safety follow-up (Visit 6) will be conducted by phone call approximately one week later. Participants may continue their study-supplied rescue salbutamol from the start of the study treatment phase until the end of the treatment period.

A participant will be considered to have completed the study when they have completed all phases of the study including screening, the treatment phase, and safety follow-up.

[figure not shown]
The total duration of participant participation will be approximately 13 weeks, 12-week treatment period and a 1-week follow-up period.

Participants that permanently discontinue study intervention are not required to withdraw from the study. If for any reason a participant must permanently discontinue study

treatment, every effort should be made by the investigator/staff to keep the participant in the study. However, a participant may voluntarily withdraw from participation in this study at any time. The investigator may also, at his or her discretion, withdraw a participant from further study participation. Participants who are withdrawn from the study will not be replaced.

Data Monitoring/ Other Committee: No

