4.4. End of Study Definition

A participant is considered to have completed the study if he/she has completed all phases of the study including screening, treatment phase and safety follow-up.

The end of the study is defined as the date of the last scheduled procedure shown in the Schedule of Activities table (SoA) (see Section 1.3) for the last participant in the study.

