7. DISCONTINUATION OF FF/UMEC/VI AND PARTICIPANT DISCONTINUATION/WITHDRAWAL

7.1. Discontinuation of FF/UMEC/VI

Participants have the right to discontinue FF/UMEC/VI before the end of the study. A participant may also be asked to discontinue FF/UMEC/VI at the Investigator's discretion.

Participants that permanently stop FF/UMEC/VI should return to the clinic as soon as possible, in order to complete the Treatment Discontinuation visit. The evaluations and procedures to be completed are outlined in the SoA (Section 1.3)

Participants that discontinue FF/UMEC/VI are encouraged to remain in the study and every effort should be made by the Investigator/staff to keep the participant in the study, to collect important efficacy and safety data.

If possible, participants should return to the clinic to complete all scheduled visits. If this isn't possible, visits should be completed by telephone. Ideally, participants should return to the clinic to complete Visit 5, to collect important spirometry data, however, if this isn't possible, this visit could be completed by telephone. A safety follow-up phone call (Visit 6) should also be conducted 7 days after Visit 5.

Following discontinuation of study intervention, if participants are unwilling to return to the clinic for their scheduled visits, the Investigator/site staff should contact the participant by telephone at the protocol designated visit time intervals to collect the following:

- SAEs
- AEs assessed as related to study participation
- AEs resulting in discontinuation of study intervention or withdrawal from the study
- COPD exacerbations
- Concomitant medication
- A safety follow-up phone call (Visit 6) should also be conducted 7 days after Visit 5.

A participant may be withdrawn from study intervention at any time. A reason for premature discontinuation of study intervention (e.g., AE, lack of efficacy, protocol deviation, Investigator discretion, consent withdrawn etc.) must be captured in the eCRF.

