9.2 Analysis

Population: SCREENED and ITT

Statistics: All above mentioned participant's disposition parameters, will be summarised (frequency & percentage) and participants listing for all participants in the study population by participant number will be provided. Screening status table will be present on screened population.

The percentage calculation of End of study/treatment classification is based on ITT population. Protocol deviation data will be summarized and listed for ITT population.

10. Participant demographics and other baseline characteristics**10.1 Variables and derivations**

The following demographic and other baseline characteristics will be summarized:

- Age
 - Number of subjects by age continuous
 - Number of subjects enrolled by age categories:
 - 18-64 Years
 - 65-84 Years
 - ≥ 85 Years
 - Missing
- Gender
- Height (cm)
- Weight (kg)

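### SAP 9.1 gives two conflicting rules for treatment completion; read literally, one counts participants who stopped FF/UMEC/VI but finished follow-up as treatment completers

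*SAP*

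**What the plan says.** SAP 9.1 (participant disposition) takes study completion from the End of Study form. It then turns to treatment completion, "And participants who completed the treatment, as indicated on the" Study Treatment Discontinuation form. An i.e. parenthetical follows at once: "participants who completed the trial will be counted under both the" completed-treatment and completed-trial categories.

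The same section lists separate lines, as per eCRF, for "Number of treatment discontinued participants" and "Reason of treatment discontinued participants". On denominators, SAP 9.2 says: "The percentage calculation of End of study/treatment classification is based on ITT population".

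The protocol separates stopping the drug from leaving the study. The Synopsis says: "Participants that permanently discontinue study intervention are not required to withdraw from the study". Protocol 7.1 says: "Participants that discontinue FF/UMEC/VI are encouraged to remain in the study". Sections 7.1.3 and 7.1.4 say the same about retention after pregnancy and after a positive COVID-19 test, both of which end study treatment. Under Protocol 4.4, a participant completes the study if he or she "has completed all phases of the study including screening, treatment phase and safety follow-up".

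**The concern.** The parenthetical is introduced as a restatement of the form-based rule, but it is not equivalent to it. A participant who stops FF/UMEC/VI in week 5, attends Visit 5 and takes the Visit 6 call has a treatment form recording discontinuation. The End of Study form may well record completion. The form-based sentence makes this person a treatment non-completer, and the parenthetical makes the same person a treatment completer. A programmer could follow either. The better retention works, the more participants fall into this group.

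Treatment discontinuation is the only key intercurrent event in both the primary and the secondary estimands. The supplementary treatment-policy estimands differ from the main ones only through participants who discontinue. The disposition table is where a reader looks to judge how much room there is for the two to differ. A treatment-completed line that is too high, or that does not fit with the discontinued line, weakens that reading.

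**Working it through.** **Inputs.** From Protocol 4.1 and 9.2: 220 evaluable participants, 4% withdrawal from study treatment, 229 enrolled to the treatment phase, 25% screen failure, 306 screened. From SAP 9.2: ITT denominator.

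**The plan's own figures.**
- Enrolled: 220 / (1 − 0.04) = 229.2. The plan states 229; strict rounding up gives 230, a difference of one participant that does not affect this point.
- Screened: 229 / (1 − 0.25) = 305.3, rounded up to 306, as stated.

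**Participants who stop treatment.** Taking the 220 as treatment completers, 229 − 220 = 9, and 9 / 229 = 3.9%. Treatment completion from the treatment form alone is therefore 220 / 229 = 96.1%.

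**Effect of the parenthetical.** Let s be the number of these 9 who are recorded as completing the study. The documents give no value for s, so it is an assumption with range 0 to 9.
- Completed line under the parenthetical: 220 + s.
- Discontinued line, if derived as the remainder: 229 − (220 + s) = 9 − s.
- Discontinued line, if read from the eCRF: 9, so the two lines add to 229 + s.

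| s | Completed line | Discontinued as remainder | Sum of lines if discontinued is read from eCRF |
|---|---|---|---|
| 0 | 220 (96.1%) | 9 (3.9%) | 229 (100%) |
| 4 | 224 (97.8%) | 5 (2.2%) | 233 (101.7%) |
| 9 | 229 (100%) | 0 (0%) | 238 (103.9%) |

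**Does the error reach any estimand?**
- The on-treatment and post-treatment AE split in SAP 14.1 uses the treatment stop date, not the disposition category.
- SAP 18.1.2 sets trough FEV1 after treatment discontinuation to missing. It does not use the disposition count.
- Protocol 9.3.1 made the supplementary FEV1 estimand depend on more than 5% of ITT participants discontinuing treatment. SAP section 4 removes that condition, so the one place where the count would have steered an analysis is gone.

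**The case against.** The strongest defence is that the sentence before the parenthetical already does what is wanted: each status comes from its own form. On that view the parenthetical is a loose gloss meaning only that the two categories are not mutually exclusive. This is a possible reading, but the words say that trial completers are counted in both categories, without exception, and nothing in the SAP says which sentence prevails.

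A second defence rests on Protocol 4.4. If completing the treatment phase means taking treatment to Day 84, every study completer is a treatment completer and the parenthetical is harmless. But Appendix 4 describes the treatment phase by visits, from Visit 2 to Visit 5. A participant who stops the drug and attends those visits could then qualify as a study completer. The protocol does not settle which meaning applies, and the SAP relies only on what the End of Study form records. This defence makes the conflict conditional but does not remove it.

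A third defence stands in full. A reader might infer that participants who stop treatment but stay in the study vanish from the treatment-discontinuation count. The documents do not support that: the number discontinued and the reasons are their own lines, as per eCRF, and the SAP nowhere derives them as whatever is left after completers. Discontinuation also remains visible in the by-participant disposition listing (SAP 9.2), the exposure summary (SAP 11) and the table of AEs leading to permanent discontinuation or withdrawal (SAP 14.2).

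**Conclusion.** The contradiction is real and the parenthetical is wrong as written for any participant who stops FF/UMEC/VI and is recorded as completing the study. At planned numbers it affects 0 to 9 of 229 participants. The treatment-completed line could read anywhere from the correct 96.1% up to 100%, or the completed and discontinued lines could add to as much as 103.9%.

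The upper end needs three things: all nine discontinuers finish the study, all nine are recorded as study completers, and the programmer follows the parenthetical over the named form. If nobody who stops treatment stays, there is no error. The range also rests on the plan's assumed 4%; a higher discontinuation rate would widen it.

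Because treatment discontinuation is the sole intercurrent event, a reader might infer that the estimand results themselves are distorted. They are not: no planned AE or FEV1 analysis takes its input from this table. The severity is low. It is a counting rule in one descriptive table that should be corrected before programming.

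**What to change.** 1. In SAP 9.1, delete the parenthetical, or limit it to participants whose Study Treatment Discontinuation form also records treatment completion.
2. State that treatment status is derived only from that form and study status only from the End of Study form, independently of each other, and that neither discontinued line is obtained by subtraction.
3. Reconcile this with Protocol 4.4 by stating whether a participant who stops treatment but finishes follow-up counts as a study completer, and make the End of Study form guidance agree.

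A two-by-two table of treatment completed by study completed would show the retained off-treatment group directly, but it is optional.

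The cost is a sentence or two in the SAP and the matching line of the programming specification. Both forms are already collected, so no new data or assessments are needed.

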9.2 Analysis

Population: SCREENED and ITT

Statistics: All above mentioned participant's disposition parameters, will be summarised (frequency & percentage) and participants listing for all participants in the study population by participant number will be provided. Screening status table will be present on screened population.

The percentage calculation of End of study/treatment classification is based on ITT population. Protocol deviation data will be summarized and listed for ITT population.

10. Participant demographics and other baseline characteristics**10.1 Variables and derivations**

The following demographic and other baseline characteristics will be summarized:

- Age
 - Number of subjects by age continuous
 - Number of subjects enrolled by age categories:
 - 18-64 Years
 - 65-84 Years
 - ≥ 85 Years
 - Missing
- Gender
- Height (cm)
- Weight (kg)

10.2 Analysis

Population: Table: ITT

Listing: ITT

Statistics: Baseline and Demographic variables will be summarized and listed by participant number. Overall summaries will include descriptive statistics for continuous measures (number of participants, mean, SD, median, minimum & maximum) and for categorical measures (frequency, percentages, and number of missing values).

11. Exposure and Compliance to study treatment

11.1 Variables and derivations

The date of first study treatment administration will be derived as the first date of dosing from the treatment administration eCRF page. The date of last study treatment administration will be derived as the date of last dose of study treatment from the treatment administration eCRF page. If this date is not available, then the date of last administration will be derived as the last date of dosing from the treatment administration eCRF page.

Interruptions, compliance, and dose changes will not be considered for calculating the duration of exposure, which will be derived as follows:

- $$\text{Duration of exposure (days)} = (\text{Date of last study treatment administration} - \text{Date of first study treatment administration}) + 1$$

Treatment compliance:

Treatment compliance will be assessed for the entire treatment period, as well as at visits 3 and 5.

If a dose counter start count is missing, then it will be assumed to be 30 for the ELLIPTA DPI. If any dose counter stop is missing, then the number of doses taken will be set to missing for that inhaler.

Number of doses of study drug taken by each participant from each inhaler = Dose counter start value – dose counter stop value.

The derivation for treatment compliance during the treatment period is defined as the sum of (dose counter start value – dose counter stop value) over all inhalers dispensed to the participant and returned during the treatment period (i.e., from study Treatment administration to EOS/EW visit) and percentage compliance will be calculated as follows:

- $$\text{Treatment compliance (\%)} = \frac{\text{Total number of doses received}}{\text{Duration of exposure (days)}} \times 100$$

Overall compliance will be categorized as follows:

- < 50 %
- $\geq 50\%$ to < 80%
- $\geq 80\%$ to < 95 %
- $\geq 95\%$ to $\leq 105\%$
- $> 105\%$ to $\leq 120\%$
- $> 120\%$

If a participant receives a treatment other than the scheduled treatment during the study, the compliance will still be calculated using data from all containers received and overall exposure start and stop dates.

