1.2. Schema

1.3. Schedule of Activities (SoA)

Protocol Activity	Pre-Screen	Screen	Treatment					Follow-up
	Visit 0	Visit 1 Screen	Visit 2	Visit 3	Visit 4 ^e (Telephon ic)	Visit 5	Study treatment discontinuation	Safety Follow-up Visit 6 ^f
Study Day			Week 0/Day 1	Week 4/Day 28	Week 12/Day 84	Week 12/Day 85		1-week Follow-up/Day 92
Window		(Day -1)		-4/+2d (Day 24 to 30)	-4/+2d (Day 80 to 86)	-4/+2d (Day 81 to 87)		-1/+4d (Day 91 to 96)
Written Informed Consent ^a	X	X						
Demography ^b	X	X						
Medical History, including cardiovascular history		X						
COPD and Exacerbation History		X						
Concomitant Medication Assessment	X	X	X	X		X	X	X
Inclusion/Exclusion Criteria		X	X					
COVID-19 test ^c		X						
Smoking History		X						
Smoking status		X				X	X	
Smoking Cessation Counselling		X				X	X	
CAT		X						
Baseline/Trough Spirometry ^d			X	X		X		
Exacerbation Assessment			X	X		X	X	X
Physical examination ^g		X				X	X	
Adverse Events Assessment		X	X	X		X	X	X
Vital signs ^h		X				X	X	
ECG		X						
Chest X-ray ⁱ		X						
Oropharyngeal examination		X				X	X	
Urine Pregnancy Test ^j		X				X	X	
Dispense study treatment			X	X				
Administer study treatment ^k			X	X	X			
Assess current COPD treatment compliance			X					

Protocol Activity	Pre-Screen	Screen	Treatment						Follow-up
			Visit 0	Visit 1 Screen	Visit 2	Visit 3	Visit 4 ^e (Telephon ic)	Visit 5	
Study Day				Week 0/Day 1	Week 4/Day 28	Week 12/Day 84	Week 12/Day 85		1-week Follow-up/Day 92
Window		(Day -1)			-4/+2d (Day 24 to 30)	-4/+2d (Day 80 to 86)	-4/+2d (Day 81 to 87)		-1/+4d (Day 91 to 96)
Assess study treatment compliance					X			X	X
Collect study treatment								X	X
Dispense salbutamol as required		X	X	X				X	
Collect salbutamol								X	X
Dispense paper Medical Problems worksheet		X	X	X				X	
Review paper Medical Problems worksheet			X	X				X	X

- a. Informed consent must be conducted prior to performing any study procedures including the changing or withholding of medications. The informed consent may be given at Screening Visit 1 if the participant does not take or has not taken any protocol excluded medications. The Pre-screen and Screening Visits can occur on the same day.
- b. Demography may be captured at either the Pre-screen Visit or Screening Visit (for participants who do not have a Pre-screen Visit).
- c. The test should be done at Visit 1, using a molecular (PCR [polymerase chain reaction] or antigen test) approved by the country regulatory authorities.

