6.1. Study Intervention(s) Administered

Participants will receive FF/UMEC/VI (see [Table 2](#)) and should inhale once from the ELLIPTA inhaler in the morning each day for the duration of the 12-week treatment period.

Table 2 Description of ELLIPTA™

FF/UMEC/VI	First strip	Second strip
FF/UMEC/VI	CC1	
Dosage Form	ELLIPTA with 30 doses (2 strips with 30 blisters per strip)	
Unit Dose Strengths	100mcg per blister	25 mcg per blister GW642444, 62.5 mcg per blister GSK573719
Physical description	Dry white powder	
Route of Administration	Inhaled	
Sourcing	Provided centrally by the sponsor	
Packaging and labelling	Each Ellipta inhaler will be labeled and placed in a labelled foil pouch with a desiccant. The foil pouch will then be placed in a window carton.	

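### SAP 11.1 scores an unreturned inhaler as missed doses, and does not say how overall compliance is formed when a returned inhaler has no stop count

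*SAP*

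**What the plan says.** SAP 11.1 defines the doses taken from one inhaler as the counter's start value minus its stop value. Three rules then bear on this point.

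- **Missing readings.** A missing start value is filled in: "If a dose counter start count is missing, then it will be assumed to be 30 for the ELLIPTA DPI". A missing stop value is not: "If any dose counter stop is missing, then the number of doses taken will be set to missing for that inhaler".
- **Numerator.** The participant's total is the sum of start minus stop "over all inhalers dispensed to the participant and returned during the treatment period".
- **Denominator.** The total is divided by the duration of exposure, which is the last dose date minus the first dose date plus 1. The SAP adds that "Interruptions, compliance, and dose changes will not be considered for calculating the duration of exposure".

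The resulting percentage goes into six bands, from under 50% to over 120%. There is no missing or not-evaluable band, although SAP 10.1 gives age a missing category and SAP 10.2 counts missing values for categorical baseline measures. SAP 11.2 plans a summary table and a participant listing on the ITT population and adds no rule for uncounted inhalers.

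**The concern.** Numerator and denominator should cover the same stretch of treatment. Here the numerator covers only inhalers that came back, while the denominator covers all days between first and last dose. An inhaler that was used but not returned adds days and no doses, so missing information appears as poor adherence. This error can only lower the percentage.

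A returned inhaler with no stop count raises a related gap. The SAP makes that inhaler's doses missing and stops there. One programmer could let the missing value carry through to the total; another could add up the remaining inhalers. SAP 6.5 names SAS, where the SUM function skips missing values and the + operator returns missing, so the choice of syntax would settle the result.

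At stake is a planned table and listing, added in SAP version 3.0 according to the revision history. A participant who took every dose could be listed as substantially non-compliant.

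**Working it through.** The documents state no compliance figure to reproduce, so the check applies the SAP formula to a participant who took every dose.

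**Inputs**

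- Dosing: Protocol 6.1 says participants "should inhale once from the ELLIPTA inhaler in the morning each day for the duration of the 12-week treatment period". One dose a day for 12 weeks is 84 doses.
- Last dose: Protocol 1.1 says "Participants will take their last dose of study treatment on Day 84", so a completer's duration of exposure is 84 days.
- Inhaler size: 30 doses (Protocol 6.1, Table 2).
- Number of inhalers: not stated. The row "Dispense study treatment" in the Schedule of Activities marks Visits 2 and 3 but gives no quantities. Since 84/30 = 2.8, at least three are needed; three is assumed.

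**Formula**

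Compliance = 100 × (doses from counted inhalers) / (duration of exposure).

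With all three inhalers counted: 84/84 = 100%, in the band from 95% to 105%.

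With exactly one uncounted and left out of the sum, the result depends on how the doses were spread across the inhalers:

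| Doses per inhaler | First uncounted | Second uncounted | Third uncounted |
|---|---|---|---|
| 30/30/24 (each emptied in turn) | 54/84 = 64.3% | 54/84 = 64.3% | 60/84 = 71.4% |
| 27/30/27 (switch at Visit 3, before the Day 28 dose) | 57/84 = 67.9% | 54/84 = 64.3% | 57/84 = 67.9% |
| 28/30/26 (switch after the Day 28 dose) | 56/84 = 66.7% | 54/84 = 64.3% | 58/84 = 69.0% |

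Every value falls in the band from 50% to under 80%.

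**Sensitivity to the assumptions**

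- Exposure of 80 to 86 days (the Visit 4 window), inhalers emptied in turn: 50/80 = 62.5% to 60/80 = 75.0% at 80 days, and 56/86 = 65.1% to 60/86 = 69.8% at 86 days. The band is the same.
- Second and third inhalers both uncounted: 27/84 = 32.1% (27/30/27) to 30/84 = 35.7% (30/30/24), in the band under 50%.
- Four inhalers, for example a switch at Visit 3 on Day 24 giving 23/30/30/1: if only the last is uncounted, 83/84 = 98.8%, and the band does not change.

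**Effect on the summary**

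The documents give no rate of uncounted inhalers. As an assumption only, suppose 1% to 10% of 229 participants have one uncounted inhaler and everyone is truly at 100%. About 2 to 23 people change band. The mean falls by between 0.01 × (100 − 71.4) = 0.3 and 0.10 × (100 − 64.3) = 3.6 percentage points.

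**The case against.** The strongest reply is that the sentence on missing stop counts does not prescribe a wrong number. It makes doses missing for one inhaler; it does not set them to zero or tell the programmer to skip them. If the missing value carries through, overall compliance is missing and no low percentage is reported. That stands. A reader might infer that the SAP orders such an inhaler to be dropped from the total. Dropping it is the more natural reading, but the text leaves the matter open. The mismatch is explicit only for unreturned inhalers.

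A reader might also infer that the Visit 3 and Visit 5 compliance counts are biased downward. SAP 11.1 and 11.2 give no visit-specific numerator or denominator, so this cannot be shown. If a single inhaler is in use up to Visit 3 and has no stop count, the Visit 3 result would be missing, not low.

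On frequency, Protocol 6.4 requires remaining doses to be recorded at site visits, and the Schedule of Activities includes compliance assessment and collection of study treatment. Uncounted inhalers may therefore be few. Against that, Protocol 7.1 lets Visit 5 be done by telephone after discontinuation, and Appendix 4 allows telephone contacts and shipment to the home during COVID-19 disruption. The trigger is foreseeable, but a material shift in the overall summary is not established.

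Finally, the consequences are narrow. There is no per-protocol or compliance-based analysis set, and neither the adverse event analysis nor the FEV1 model uses compliance. A reader might infer that the primary or secondary results are affected; the documents do not support that.

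**Conclusion.** The point holds in limited form. For an unreturned inhaler, SAP 11.1 as written removes the doses and keeps the days, so unknown use is scored as non-use. For a returned inhaler with no stop count, the rule is incomplete, and one of its two readings gives the same error.

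For a fully adherent participant the reported figure would be about 64% to 71% instead of 100%. This rests on 84 days of exposure, three inhalers and exactly one uncounted; for the missing stop count it also requires that the total skip that inhaler. How many participants would be affected is unknown. The effect is confined to the overall compliance summary, its categories and the listing. Severity is minor.

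**What to change.** In SAP 11.1, state that if any dispensed inhaler was not returned or has no usable stop count, overall compliance is set to missing. Add a not-evaluable row to the category table with the number of participants concerned. One rule then covers both situations, and the bands plus the new row account for the whole ITT population.

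The cost is one sentence and a small programming change. The affected participants will have no compliance value, so the summary describes only those with complete counts; the new row shows how many are left out.

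Removing the uncounted inhaler's days from the denominator would also restore the match (54/54 or 60/60 = 100%). It needs dates of use for each inhaler, which the documents do not describe: Protocol 6.4 records dates and times for doses given in clinic and relies on questioning and counter readings for home dosing. Setting the value to missing is the more workable choice.
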